1. INTRODUCTION

The purpose of this trial is to find out if a short course of antibiotics will treat chronic endometritis and reduce miscarriage in women who have experienced two or more consecutive miscarriages. Endometritis is an inflammation of the endometrium (lining of the womb). The group of microorganisms that live in our bodies is called the microbiome and if there is an imbalance of the microbiome (dysbiosis) in the reproductive tract this may cause inflammation of the endometrium. The endometrium is important for implantation of the ovum (egg and sperm) and to support the fetus as it develops. Endometritis may disrupt implantation and lead to miscarriage. Endometritis has been linked to miscarriage and it is suggested that reducing the inflammation, with a course of antibiotics, will reduce miscarriages.

1.1 Background

1.1.1 Epidemiology and burden of the condition

Recurrent miscarriage (RM) causes considerable distress and psychological morbidity for women and their partners. The vast-majority of couples receive supportive care only, as few treatments have been shown to prevent miscarriage. The patient-led James Lind Alliance priority setting partnership has identified '*effective interventions to prevent miscarriage*' as a number one research priority.¹

1.1.2 Chronic Endometritis and Recurrent Miscarriage

A healthy endometrium is important for successful implantation and support of the developing fetus. The bacteria that colonise the endometrium and vagina, known as the microbiome, play an important role in the endometrial health. Dysbiosis, an imbalance of the microbiome may cause inflammation of the endometrium, known as Chronic Endometritis (CE) and lead to miscarriage. Antibiotics can reduce this inflammation; although this treatment is available at private clinics and in some European countries, there is no robust evidence to support this approach and the effect of antibiotics on the microbiome is unclear.

1.1.3 Diagnosing Chronic Endometritis

Initially, the diagnosis of chronic endometritis was based on Haematoxylin and Eosin (H&E) staining of tissue sections,² but the identification of plasma cells on morphology alone is cumbersome and associated with substantial significant inter-observer variation. During differentiation, plasma cells acquire expression of CD138 (syndecan-1). Immunohistochemistry (IHC) with antibodies to CD138 reliably identify plasma cells³ with increased sensitivity,⁴ increased concordance between pathologists,⁵ and reduced inter- or intra-observer variability when compared to H&E staining.⁶ Thus, IHC is now the method of choice for identification of plasma cells. Plasma cells are not normally present in high numbers in normal endometrium.

1.1.4 Chronic Endometritis and the Microbiome

CE is thought to be caused by the presence of an array of microorganisms and a lack of lactobacilli in the endometrium, an imbalance termed dysbiosis.⁷⁻¹¹ Three separate studies reported that a two-week course of the antibiotic doxycycline 'cured' CE in over 90% of cases.⁹

¹²⁻¹⁴ Additionally, non-randomised, observational studies suggest that treating CE with doxycycline prevents miscarriage.⁹ ^{12 15 16}

1.1.5 Evidence that CE is a treatable cause of miscarriage

Our systematic review did not identify any RCTs of the use of antibiotics for the treatment of CE or for the prevention of miscarriage. Meta-synthesis of non-randomised studies of women with reproductive failure, from any cause, revealed that the prevalence of CE varies between 9%-57%; reflecting the different methods and criteria used for diagnosis. Our analysis of live births in non-randomised cohort studies in women who conceived following a diagnosis of CE indicated that:

- The live births versus miscarriages in treated versus untreated CE could not adequately be assessed as the studies were too small to reliably identify important differences.^{15 16}
- 2. The live birth following treatment of CE was similar to that of patients without CE. These data imply that treating CE improves the live birth rate to that of women with no CE. However, these studies were small, single centre, non-randomised and used varying treatment regimens.
- **3.** There are more live births in women treated for CE which resolved than in those in whom the CE persisted after treatment again suggesting a positive effect of treatment but in observational studies only.

1.1.6 Evidence of endometrial microbiome dysbiosis in CE

Although the pathophysiology of CE is poorly understood, the presence of plasma cells is thought to reflect either chronic infection or chronic inflammation.² It has been suggested that the presence of plasma cells reflects an immune response to pathogens within the uterine cavity that ascended from the lower genital tract.¹⁷ Several studies have sought to identify and characterise these microorganisms; however, recent application of cultureindependent sequencing approaches demonstrated that the endometrium is not a sterile environment, as previously believed.¹⁸ Instead the endometrium harbours its own unique microbiome.¹⁹ This has been replicated in other tissues previously believed to be sterile, including the lung, placenta²⁰ and lower urinary tract.²¹ As such the identification of organisms may not represent pathological colonisation but rather a healthy balance of microorganisms that are essential for the optimal function of the endometrium. Dysbiosis of the endometrial microbiome may account for plasma cell infiltration in CE. Next Generation Sequencing (NGS) of bacterial 16S ribosomal RNA genes has been undertaken to characterise the endometrial microbiome. Like the vaginal microbiome, the endometrium is typically dominated by Lactobacillus spp.²² ²³ The endometrial microbiota of patients undergoing Assisted Reproduction Techniques (ART) was found to be similar to that of the vagina.^{8 24} However, differences in the vaginal and endometrial microbiome imply they are not merely a continuation of each other, but distinct environments with a similar yet unique microbiome.²⁴ Compared to a normal endometrial microbiome (>90% Lactobacillus spp), Lactobacillus spp. depletion (<90%) is associated significantly poorer with ART outcomes implantation,60%v33%p=0.03, on-going pregnancy, 59% v13% p=0.02 and live birth rates, 58% v 7% p=0.002).²⁴

A comparison of the microbial profile in recurrent implantation failure patients demonstrated that those with CE had a higher detection rate of specific species, including *Corynebacterium*

(RR, 19.60) and Mycoplasma hominis (RR,5.04), compared to those without CE.^{9 25} Another trial focussing on endometrial polyps reported that the endometrial microbiome was more diverse in CE confirmed by IHC.⁸ Further, using the less sensitive culture techniques, organisms were detected in 73% of CE cases,⁷ Ureplasma uraelyticum in 10% and Chlamydia trachomatis was 2.7%.⁷ Using sequencing techniques the presence of these organisms detected by culture was associated with a reduction in Lactobacillus spp., indicative of dysbiosis¹⁰ and poor pregnancy outcomes.¹¹

1.1.7 Evidence of the impact of CE on endometrial function

Our literature search identified no studies on how CE impacts on endometrial function. RM is associated with inadequate preparation of the endometrium for pregnancy, a process termed decidualisation.²⁶ Because of menstruation, decidualisation is a reiterative process, linked to cyclic activation of mesenchymal stem-like cells (MSCs) and their subsequent differentiation into mature stromal cells in regenerating endometrium.^{26 27} Clinically, endometrial MSC deficiency,²⁷ heightened cellular senescence, prolonged inflammation^{26 28} and impaired decidualisation potential of endometrial stromal cells²⁹ are strongly linked to RM, but whether or not these defects are caused by CE is not known.

1.1.8 Evidence of efficacy of doxycycline treatment

The most frequently used antibiotic regime in published studies is doxycycline (100mg twice daily for 14 days). Based on analysis of repeat endometrial biopsies, a single course of doxycycline was reported to 'cure' histologically defined CE in 92%,⁹ 94%¹² 75%,¹³ and 70%¹⁴ of patients. Following doxycycline treatment, changes to the endometrial microbiome have been identified. Notably, the detection rates of Corynebacterium, Enterococcus, Escherichia coli, Streptococcus agalactiae, Ureaplasma urealyticum and Ureaplasma parvum were significantly lower following antibiotic treatment.⁹ This reduction in pathogenic microorganisms was associated both with a significant increase in Lactobacillus spp, the major resident species within the uterine cavity³⁰ and a reduction in the number of plasma cells within the endometrial stromal compartment.⁹ This suggests a shift towards a normal microbiota following doxycycline treatment. Importantly, no trial to date reported on the persistence of CE on repeat biopsies in non-treated women. We found that \geq 12 CD138+ cells/mm2 persisted in only 78% of untreated women when biopsied again after two or more cycles (n=32).

These observations suggest that CE may resolve spontaneously, or be intermittent, in some women but persists in others. Further, in addition, to its antibacterial properties, doxycycline has a well-documented anti-inflammatory effect,³¹ raising the possibility that it is useful for the treatment of CE not associated with endometrial symbiosis.

1.2 Proposed trial

A prospective, multi-centre, randomised, double blind adaptive designed trial, comparing a pre-conception 14 day course of doxycycline to placebo in up to 1500 women with recurrent miscarriage associated with chronic endometritis.

1.3 Target population

Women aged between \geq 18 to <42 at registration who have experienced two or more consecutive first trimester miscarriages.

1.4 Chronic Endometritis Diagnosis

Chronic Endometritis will be diagnosed based on the density of CD138 staining cells within a tissue section of the biopsy. A positive screen will be defined as \geq 5 CD138 positive cells per 10mm².

1.5 Treatment

Women who screen positive for CE, are eligible and wish to participate will be randomised to either doxycycline 100 mg or matching-placebo twice a day for 14 days.

2. RATIONALE

2.1 Aims and hypothesis

The aim in this trial is to determine if doxycycline administered prior to conception improves pregnancy outcome in women with recurrent miscarriage associated with chronic endometritis and explore the mechanisms by which it could prevent miscarriage.

2.2 Justification

There is increasing evidence in the literature that CE is a treatable cause of RM. CE is persistent inflammation of the endometrium, detected by the presence of plasma cells in the endometrium and linked to miscarriage. The incidence and nature of endometrial dysbiosis associated with CE in RM has not been studied systematically; nor is it known if CE in RM is associated with sterile inflammation or chronic dysbiosis. It is not known if CE causes or compounds the endometrial defects associated with RM. It is also not known if resolution of CE, in response to doxycycline treatment, reverses endometrial defects.^{27 32 33} Observational studies suggest that antibiotic treatment may be effective in preventing miscarriage in women with CE, but this has not been tested in a randomised double-bind placebo controlled trial. Our observations suggest that CE may resolve spontaneously in some women but persists in others. Hence, there is a genuine need for placebo-controlled trial to determine the efficacy of doxycycline treatment on the subsequent on-going pregnancies in women with recurrent miscarriage associated with chronic endometritis.

2.3 Assessment and management of risk

A risk assessment has been completed by the Sponsor. The risk assessment will cover all risks associated with the trial and trial management. It will be updated on a continual basis as the risks change throughout the life of the trial.

2.3.1 Risk of Pregnancy

In the summary of product characteristics (SPC) doxycycline is contra-indicated in pregnancy, because tetracycline use has been associated with problems with infant's teeth and bone development. However, a meta-analysis by Cross and colleagues (2016)³⁴ reported an absence of evidence of harmful effects when taken in pregnancy and there are no known reported cases or evidence of harm from taking doxycycline from day 1 to 14 of the menstrual cycle. Doxycycline is prescribed to pregnant women "when travel to malarious areas is unavoidable during pregnancy, doxycycline can be used for malaria prophylaxis if other regimes are unsuitable, and if the entire course of doxycycline can be completed before 15 weeks' gestation" (BNF, 2018-2019). This trial has been designed so there is minimal chance of fetal exposure in the following ways:

- **1.** A pregnancy test is performed prior to taking doxycycline
- **2.** Doxycycline/placebo is taken on the first day of the menstrual cycle so women are not pregnant when they start taking the intervention
- **3.** The doxycycline/placebo are taken prior to ovulation, hence before pregnancy is possible we review all women's cycles
- 4. Women are advised and consent to use condoms
- **5.** The half-life of doxycycline is 16-22 hours thus there will be minimal drug present one week after the drug is stopped should implantation occur.¹⁰

The doxycycline/placebo will start on the first day of their next menstrual cycle. We plan to start the intervention on day one of the cycle to ensure that the treatment is completed during the proliferative phase of the cycle, thus negating the risk of doxycycline exposure in early pregnancy.

If a participant reports she is pregnant during the month they are taking the doxycycline/placebo, they will discontinue taking the doxycycline/placebo and will be reassured that the risk to her infant is extremely small.

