6.2 Exclusion criteria – screening

- Treatable cause(s) of RM for example:
 - o antiphospholipid antibody syndrome
 - o thyroid disease
 - parental karyotypical abnormalities.
- Known sub-septate uterus.
- Poorly controlled diabetes (HbA1c >48mmol/mol)
- Allergy to doxycycline or its excipients.
- Doxycycline contraindicated
- Antibiotics in the current menstrual cycle
- Taking a medication that may interact with doxycycline refer to table 8 for a full list.
- Myasthenia Gravis.
- Systemic lupus erythematosus (SLE).
- Immunodeficiency disorder.
- Alcohol dependency*
- Long-term antibiotic(s) use.
- Menstrual cycle $\leq 21 \geq 42$ days.
- Unable to give informed consent.
- Participation in another clinical trial of an investigational medicinal product (CTIMP) in the last 90 days.
- Women who are breast feeding.
- Pregnancy

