7.6.2 Consent to participate in the RCT CERM B

Women attending the UHCW site will be asked to consent to the CERM B RCT. These participants will consent to having a second endometrial biopsy and vaginal, endometrial and cervical swabs being taken.

Following consent the site research team should ensure that participants have been given a copy of the signed CERM B RCT informed consent form and PIS.

Screen-positive women in CERM B will have a biopsy during the luteal phase (10 ± 4 days) after ovulation during the intervention cycle. CERM B participants should be provided with a second biopsy preparation kit. The preparation, procedure and analysis will be identical to the first biopsy procedure (see the tissue samples section of the protocol for further details).

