7.7 Randomisation – Randomised Controlled Trial

The trial ID number allocated during registration will be used as part of the randomisation process.

Sites should log on to the CERM registration/randomisation portal to randomise the participant and obtain a drug pack number. Sites should access the portal via the link below:

https://ctu.warwick.ac.uk/CERM

In the unlikely event the registration/randomisation portal is not available please contact the WCTU CERM Trial Team (contact details given in table 4) who will be available week days between 09:00 and 17:00 (16:00 on Fridays).

Women will be randomised using minimisation, balancing age and number of previous miscarriages, as these are the two most important predictors of pregnancy outcome in women with RM.

An email will be sent to the PI and lead contact at site confirming participant randomisation details, trial ID number and participant drug pack number.

Following randomisation the site research team should ensure that the participant's details are updated onto the local site's participant enrolment Log.

Once a participant is randomised they should be provided with the 'Taking my capsules on the CERM trial: Chronic Endometritis and Recurrent Miscarriage' leaflet and instructed as follows:

- Take one capsule, twice a day, 12 hours apart for 14 days starting on day one of their menstrual cycle.
- Use condoms and to not have unprotected sexual intercourse during their entire menstrual cycle and not just whilst taking the doxycycline/placebo. This is the last cycle women will be asked to use condoms and to not have unprotected sexual intercourse.
- Given a CERM Trial participant card. This should be carried with the participant at all times. If a replacement is needed they should contact their local site research team.
- Participants should be reminded to undergo a urine pregnancy test as soon as their menstrual periods are delayed or a pregnancy is suspected and to contact the site research team immediately.

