8.6 Dosage schedules

8.6.1 Dose

All participants should take Doxycycline 100mg/placebo twice a day orally for 14 days starting on day one of participants' menstrual cycle.

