9.4.1 CERM B participant post treatment completion – UHCW ONLY

In addition to the assessments listed in section 9.4 CERM B participants (n^{200}) will undergo the following assessments 10 (+/- 4) days after ovulation following treatment completion:

- Pregnancy test
- Period review
- Endometrial Biopsy
- Vaginal Swab
- Endometrial Swab
- Cervical Swab

The UHCW research team will keep in regular contact with these participants.

Participants should be asked to bring in their treatment diary and any unused medication. Treatment completion assessments listed in 9.4 will be competed at this visit.

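### The protocol says that day 1–14 dosing ends before ovulation and so removes early-pregnancy exposure, but this does not hold for the shortest eligible cycles

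*Protocol*

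**What the plan says.** Protocol section 2.3.1 notes that the product characteristics contraindicate doxycycline in pregnancy. It then lists five reasons why fetal exposure should be minimal:

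1. a pregnancy test before treatment;
2. a start on the first day of the cycle;
3. timing relative to ovulation: "The doxycycline/placebo are taken prior to ovulation, hence before pregnancy is possible we review all women's cycles";
4. condom use;
5. a half-life of 16–22 hours, so that little drug is left one week after stopping, should implantation occur.

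The paragraph after the list adds that starting on day one is planned to "ensure that the treatment is completed during the proliferative phase of the cycle, thus negating the risk of doxycycline exposure in early pregnancy".

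The dosing schedule is the same for everyone. Section 8.6.1 has the capsules taken "twice a day orally for 14 days starting on day one of participants' menstrual cycle", section 7.7 gives participants the same instruction, and section 8.7 permits no dose delays.

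On cycle length, the screening exclusion in section 6.2 reads "Menstrual cycle $\leq 21 \geq 42$ days". Cycles of 22 to 41 days are therefore eligible. The randomisation criteria in sections 6.3 and 6.4 add no limit on cycle length or ovulation day.

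**The concern.** Item 3 and the paragraph after the list are stated without qualification, as though a day-one start guaranteed that the last capsule comes before ovulation. Whether it does depends on when ovulation falls, and that depends on cycle length. A fixed course ending on day 14, combined with eligibility from 22 days, makes the guarantee doubtful at the short end.

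Item 5 leans on the same premise. A week between the last capsule and implantation is available only if dosing stops at about ovulation or earlier.

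What is at stake is the accuracy of the pregnancy-risk rationale for a drug that the protocol itself describes as contraindicated in pregnancy. If the timing argument fails for some eligible women, condom use is the listed measure left to prevent conception during the dosing cycle. Sections 7.3 and 16.2 both anticipate that condoms may fail or not be used.

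**Working it through.** **Inputs from the protocol**
- Last dosing day: cycle day 14 (7.7, 8.6.1), with no delays (8.7).
- Eligible cycle length L: 22 to 41 days (6.2).
- Half-life h: 16 to 22 hours (2.3.1).

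**Assumptions, because the protocol does not give the figures**
- Luteal length P is varied over 10, 12, 14 and 16 days. For orientation, sections 7.3 and 7.6.2 time the luteal-phase biopsy at 10 ± 4 days after ovulation, so the protocol itself allows for luteal sampling up to 14 days after ovulation.
- Implantation is taken as about 7 days after ovulation. This is how the one-week argument in 2.3.1 works if dosing stops at about ovulation.

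**Step 1: the protocol's own half-life statement.** The fraction remaining after t hours is 2^(−t/h). At 7 days (168 hours) it is 2^(−168/16) = 0.07% for h = 16 and 2^(−168/22) = 0.5% for h = 22. The statement that little drug remains after one week is correct.

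**Step 2: does dosing end before ovulation?** Ovulation day = L − P. Dosing days after ovulation = 14 − (L − P).

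| Luteal length P | Ovulation day when L = 22 | Dosing days after ovulation when L = 22 | Eligible cycles with ovulation before day 14 |
|---|---|---|---|
| 10 | 12 | 2 | 22–23 days |
| 12 | 10 | 4 | 22–25 days |
| 14 | 8 | 6 | 22–27 days |
| 16 | 6 | 8 | 22–29 days |

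With P = 14, cycles of 22, 23, 24, 25, 26 and 27 days have 6, 5, 4, 3, 2 and 1 dosing days after ovulation. At 28 days the last dosing day is the ovulation day.

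For the pre-ovulation statement to hold at L = 22, ovulation must come after day 14: 22 − P > 14, so P < 8 days.

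**Step 3: what becomes of the one-week gap?** In a 22-day cycle, implantation day = (22 − P) + 7, and the gap is counted from day 14.

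| P | Implantation day | Gap after last dosing day | Remaining, h = 16 | Remaining, h = 22 |
|---|---|---|---|---|
| 10 | 19 | 5 days | 0.6% | 2.3% |
| 12 | 17 | 3 days | 4% | 10% |
| 14 | 15 | 1 day | 35% | 47% |

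With P = 16 the assumed implantation day is 6 + 7 = 13, before dosing ends. With P = 14 and a 28-day cycle, the gap is (28 − 14) + 7 − 14 = 7 days, and the result of step 1 is recovered.

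**Step 4: does another passage resolve it?** Section 2.3.1 says that cycles are reviewed, and Table 5 and section 9.3 list a period review at randomisation. No rule connects either review to eligibility or to the dosing course beyond the 22–41 day range.

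**The case against.** The strongest reply is that section 2.3.1 claims overall only a minimal chance of fetal exposure, and supports it with several measures. Just two of the five listed items, 3 and 5, depend on ovulation timing. The pregnancy test, the day-one start and the condom requirement do not, and condoms are required throughout the intervention cycle (7.7), not only on dosing days. Treatment also stops if pregnancy is reported. All of this stands. A reader might infer that the protocol exposes early pregnancies to doxycycline; the document does not support that, and it does not say what share of women have short cycles.

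It is also fair to object that 22–27 days is not a fact in the protocol. It follows from an assumed 14-day luteal phase, and the range narrows to 22–23 days at 10 days. Likewise 35–47% is an unfavourable corner of the calculation, not a typical value. Both objections stand and are why ranges are given. Neither removes the conflict, since every luteal length tried leaves some eligible cycles affected.

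A further inference would be that the CERM B second biopsy is compromised, because section 7.6.2 places it "after ovulation during the intervention cycle" and in a 22-day cycle with a 14-day luteal phase that window opens on day 14, a dosing day. The document does not support this. Section 9.4.1 asks for samples "10 (+/- 4) days after ovulation following treatment completion", and the two sections can be met together: in that same cycle, days 15 to 22 satisfy both. Sampling on drug would be a departure from 9.4.1, not something the plan calls for.

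**Conclusion.** The concern holds as an internal contradiction. The unqualified statements in section 2.3.1 are not true for all women whom section 6.2 admits under the fixed course in sections 7.7 and 8.6.1. The affected eligible cycles run from 22 days up to 23, 25, 27 or 29 days, for assumed luteal phases of 10, 12, 14 or 16 days.

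Item 5 is weakened in the same cycles. At the 22-day extreme, the remaining fraction ranges from 0.6–2.3% to 35–47% for luteal phases of 10 to 14 days, conditional on implantation about a week after ovulation.

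The finding is limited to the timing safeguard, which the design does not deliver in short cycles. It does not show that exposure will occur, and no sample size, power or error-rate figure depends on it.

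**What to change.** Reconcile section 2.3.1 with sections 6.2, 7.7 and 8.6.1. Either the pre-ovulation statement and the claim that early-pregnancy risk is removed become true for every eligible woman, or they are restated to say what holds in short cycles and which of the remaining safeguards apply there. The half-life item should be worded consistently with whichever is chosen. Which passage changes is a clinical decision for the sponsor, and no cycle limit or schedule is suggested here.

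If the risk statement is reworded, the cost is a change of protocol text, and the statement may become less favourable. If another passage is changed instead, its practical cost depends on what the sponsor decides.
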